5.5.7 Dose Modifications for Other Adverse Events

Dose interruption and modification guidelines for other adverse events are in Table 2. Lenalidomide should be held for any ≥ grade 3 adverse events with suspected drug association until resolution to < grade 2. For any patient who does not experience resolution to < grade 2 within 6 weeks should be removed from protocol treatment and complete all off-study evaluations. For patients with thromboembolic events, both agents should be discontinued and not resumed until resolution with proper prophylaxis according to the discretion of the treating investigator.

NOTE: Patients will be removed from study treatment if lenalidomide is held for > 6 weeks for treatment-related toxicity.

NOTE: For patients on Arm B, epoetin alfa will continue while lenalidomide is being held for toxicity.

Rev. 1/10

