5.2 Cross-Over Treatment

Patients who fail to achieve a MER on Arm A AND patients on Arm A who relapse will be offered to cross over to Arm B to receive combined treatment in the absence of limiting toxicity precluding continuation of lenalidomide treatment. The dose for Arm B crossover is the dose of lenalidomide that would otherwise be implemented for continuation of therapy according to Section [5.5](#). If a patient does not choose to cross over, he/she will then discontinue study treatment.

Response to cross-over treatment will be assessed after 16 weeks (4 cycles) of combined therapy (i.e., study week 32). Arm A patients that cross over to Arm B that do not achieve a MER after 16 weeks of combined treatment (i.e. week 32) will discontinue protocol treatment.

Rev. 6/14

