⁷ Serious tumor flare reactions have been observed in patients with chronic lymphocytic leukemia (CLL) and lymphoma.

⁸ A decrease in the number of stem cells (CD34+ cells) collected from patients treated with >4 cycles of lenalidomide has been reported.

⁹ Significantly increased risk of deep vein thrombosis (DVT), pulmonary embolism (PE), and arterial thrombosis has been observed in patients with multiple myeloma receiving lenalidomide with dexamethasone.

¹⁰ Gastrointestinal hemorrhage includes: Anal hemorrhage, Cecal hemorrhage, Colonic hemorrhage, Duodenal hemorrhage, Esophageal hemorrhage, Esophageal varices hemorrhage, Gastric hemorrhage, Hemorrhoidal hemorrhage, Ileal hemorrhage, Intra-abdominal hemorrhage, Jejunal hemorrhage, Lower gastrointestinal hemorrhage, Oral hemorrhage, Pancreatic hemorrhage, Rectal

hemorrhage, Retroperitoneal hemorrhage, and Upper gastrointestinal hemorrhage under the GASTROINTESTINAL DISORDERS SOC.

¹¹ Gastrointestinal obstruction includes: Colonic obstruction, Duodenal obstruction, Esophageal obstruction, Ileal obstruction, Jejunal obstruction, Obstruction gastric, Rectal obstruction, and Small intestinal obstruction under the GASTROINTESTINAL DISORDERS SOC.

¹² Osteonecrosis of the jaw has been seen with increased frequency when lenalidomide is used in combination with bevacizumab, docetaxel (Taxotere®), prednisone, and zoledronic acid (Zometa®).

NOTE: While not observed in human subjects, lenalidomide, a thalidomide analogue, caused limb abnormalities in a developmental monkey study similar to birth defects caused by thalidomide in humans. If lenalidomide is used during pregnancy, it may cause birth defects or embryo-fetal death. Pregnancy must be excluded before start of treatment. Prevent pregnancy during treatment by the use of two reliable methods of contraception.

NOTE: In a trial of first line treatment of patients with chronic lymphocytic leukemia (CLL), single agent lenalidomide (CC-5013) increased the risk of death as compared to control arm (chlorambucil).

NOTE: In two randomized trials of patients with multiple myeloma (MM), the addition of MK-3475 (pembrolizumab) to a thalidomide analog plus dexamethasone, resulted in increased mortality. Treatment of patients with MM with a PD-1 or PD-L1 blocking antibody, such as MK-3475 (pembrolizumab), in combination with a thalidomide analog, such as lenalidomide, is not recommended outside of controlled clinical trials.

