5.5.8 Dose Reduction for Patients with Renal Insufficiency

Defined as creatinine >1.5 mg/dl that does not resolve to grade 1.

Rev. 6/11

[Deleted in Addendum #4]

- Patients with CLcr <60 mL/min and ≥ 30 mL/min should be monitored closely for possibly excess myelosuppression or other toxicity, and dose reduce by 50% upon recovery.

Rev. 6/11

[Deleted in Addendum #4]

Table 2: Dose Modifications for Lenalidomide

System	NCI CTCAE Grade	Action
Coagulation	Venous thrombosis/embolism ≥ Grade 3	
 Hold (interrupt) dose and start anticoagulation; resume lenalidomide at investigator's discretion (maintain dose level).
Skin	Desquamating (blistering) rash	
 Discontinue study treatment.
	Non- desquamating rash Grade 2	
 If Grade 2, interrupt lenalidomide therapy. Resume lenalidomide when the rash resolves to ≤ Grade 1 (decrease one dose level).
	Grade ≥ 3	
 Hold lenalidomide study drug.
Neurology	Neuropathy Grade 3	
 If Grade 3, interrupt lenalidomide 3 therapy. Resume lenalidomide when the neuropathy resolves to ≤ Grade 1 (decrease one dose level).
	Grade 4	
 Hold lenalidomide study drug.
Allergy	Allergic reaction Grade 2	
 If Grade 2, interrupt lenalidomide therapy. Resume lenalidomide when symptoms resolve to ≤ Grade 1 (decrease one dose level).
	≥ Grade 3	
 Hold lenalidomide study drug.
Gastrointestinal	Constipation ≥ Grade 3	
 Hold (interrupt) dose. Initiate bowel regimen, and resume lenalidomide when constipation resolves to ≤ grade 2 (decrease one dose level).
Endocrine	Hyperthyroidism or hypothyroidism	
 Interrupt lenalidomide and initiate appropriate medical therapy. Resume lenalidomide at investigator's discretion (maintain dose level).
Cardiac Arrhythmias	Sinus bradycardia/other cardiac arrhythmia Grade 2	
 Hold (interrupt) dose. Follow at least weekly. If the toxicity resolves to ≤ grade 1 resume at next lower dose level.
	≥ Grade 3	
 Hold lenalidomide study drug.

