Other Toxicity	Other non-hematologic toxicity assessed as lenalidomide-related ≥ Grade 3	
 Hold (interrupt) dose. Follow at least weekly. If the toxicity resolves to ≤ grade 2 resume at next lower dose level.

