8.2.10 Side Effects

1. Fever (29%).
2. Gastrointestinal: Diarrhea (21%), nausea (17%), vomiting (17%).
3. Cardiovascular: Edema (17%), hypertension with dialysis patients.
4. Neurologic: Paresthesia (11%); increased incidence of seizures in dialysis patients.
4. Dermatologic: Local erythema; rash (mild, rare, and transient).

Rev. Add15

Rev. 6/13

Rev. 5/17

Rev. Add15

5. Thrombotic events: Pulmonary embolism, cerebral vascular accident.
6. Other: Potential to increase tumor growth.

Thrombovascular Events

TVEs, such as myocardial ischemia, myocardial infarction, cerebrovascular accidents (cerebral hemorrhage and cerebral infarction), transient ischemic attacks, deep venous thrombosis, arterial thrombosis, pulmonary emboli, retinal thrombosis, and clotting of an artificial kidney or shunt have been associated with the use of erythropoietic agents as reflected in the labeling of all currently marketed products. Additionally, there is a potential for an increased rate of TVE occurrence when recombinant human erythropoietin is used in non-anemic subjects. Published findings from a study evaluating survival in subjects with cancer has indicated that there may be an increased risk of TVE associated with recombinant human erythropoietin treatment of non-anemic cancer subjects.¹⁰

In summary, the occurrence of TVE is associated with epoetin alfa treatment whether used in anemic or non-anemic subjects.

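### Section 5.5.7 stops both agents after a thromboembolic event, but its closing NOTE on continuing epoetin alfa has no thromboembolic exception, and the Table 2 coagulation row does not match

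*Combined protocol and SAP*

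**What the plan says.** Three pieces of current text bear on a thromboembolic event in a patient receiving both drugs.

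- **Section 5.5.7, body.** Once a thromboembolic event has occurred, the instruction is "both agents should be discontinued and not resumed until resolution with proper prophylaxis according to the discretion of the treating investigator". The sentence sets no grade threshold and does not separate venous from arterial events.
- **Section 5.5.7, closing NOTE.** For patients on Arm B, "epoetin alfa will continue while lenalidomide is being held for toxicity". No exception is stated.
- **Table 2, coagulation row** (printed after 5.5.8, but named in 5.5.7 as the place where the guidelines are found). For "Venous thrombosis/embolism ≥ Grade 3" the action is "Hold (interrupt) dose and start anticoagulation; resume lenalidomide at" the investigator's discretion, with the dose level maintained. The table is titled as a lenalidomide table and gives no action for epoetin alfa.

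The NOTE also reaches crossover patients. Under section 5.2, Arm A patients without a major erythroid response, or who relapse, "will be offered to cross over to Arm B to receive combined treatment in the absence of limiting toxicity" that precludes further lenalidomide.

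**The concern.** The NOTE and the body sentence give opposite epoetin alfa instructions for the same event, and the protocol states no order of precedence between them.

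The stake is dosing safety. Section 8.2.10 says that "the occurrence of TVE is associated with epoetin alfa treatment whether used in anemic or non-anemic subjects", so the drug in question is one the protocol itself links to the event. The protocol also guards against this toxicity more closely than others:

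- Section 3.1.1.22 excludes patients with an event in the preceding 3 years.
- Section 1.3 rules out aspirin prophylaxis.
- Section 5.3.6 requires expedited reporting of every event of grade 3 or higher, whatever its attribution.
- Section 9.4.1 closes accrual if 2 or more of the first 30 patients treated in an arm have an event of grade 3 or higher.

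A site that applied Table 2 and then the NOTE could give further weekly injections after a clot and believe that it was following the protocol.

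**Working it through.** No arithmetic applies. The check traces one case through the rules and then looks for text that settles the conflict.

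**Case: an Arm B patient with a grade 3 venous thrombosis.**

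| Step | Source | Lenalidomide | Epoetin alfa |
|---|---|---|---|
| 1 | 5.5.7, body sentence | Stop; no restart before resolution with prophylaxis | Stop; same condition |
| 2 | Table 2, coagulation row | Hold, anticoagulate, resume at discretion | Not mentioned |
| 3 | 5.5.7, closing NOTE | Already held for toxicity under step 2 | Continue |

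Steps 2 and 3 together continue epoetin alfa. Step 1 stops it. On lenalidomide, steps 1 and 2 agree on interruption, on antithrombotic cover and on investigator discretion. They differ in that only step 1 makes resolution a condition of restarting.

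**Does the choice of verb remove the conflict?** One could argue that a drug that is discontinued is not being held, so the NOTE is never triggered. That does not work. The body sentence itself provides for resumption, so it describes an interruption. Table 2 uses the word hold for this event, and a hold is what triggers the NOTE. The general rule in 5.5.7 also holds lenalidomide for events of grade 3 or higher with suspected drug association.

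**Does other text settle it?**

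- Section 5.5.5 gives the epoetin alfa dose rules, and they depend on hemoglobin only.
- Section 5.3.6 covers reporting.
- Section 8.2.10 describes the risk, and 8.2.11 asks staff to monitor for thrombosis. Neither says whether to stop the drug.
- Section 5.7.3 leaves discontinuation to the investigator's judgment of severe or permanent harm.
- Section 9.4.1 governs accrual, not the treatment of the individual patient.

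None of these says which of the two 5.5.7 instructions prevails.

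**The case against.** The strongest reply is that a specific rule displaces a general one. The body sentence names thromboembolic events and both drugs. The NOTE deals with the ordinary case in which lenalidomide alone is interrupted. Both stand in one short section, so a site would have to read the NOTE and overlook the end of the paragraph above it. Table 2 is a lenalidomide table, so its silence on epoetin alfa is natural. Its instruction to anticoagulate sits well with the prophylaxis that 5.5.7 asks for. Expedited reporting and the early stopping rule make unnoticed harm less likely.

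Most of this stands. The specific sentence is the likeliest reading, and a careful physician would probably stop both drugs. But the NOTE is the more specific text on arm and agent, it comes last, and it is unqualified. The reporting and stopping rules act after the event and do not tell the site what to do with the next injection.

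Three stronger readings are tempting, and the documents do not support them.

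- **That the protocol orders epoetin alfa to continue through every lenalidomide hold.** The NOTE carries no exception, but it does not say that it applies without exception, and the body sentence says the opposite for this event.
- **That arterial events fall into a separate gap.** The coagulation row is venous only, and footnote 9 of section 5.4 says "Significantly increased risk of deep vein thrombosis (DVT), pulmonary embolism (PE), and arterial thrombosis has been observed". That footnote concerns multiple myeloma patients receiving lenalidomide with dexamethasone. More to the point, the 5.5.7 sentence already covers thromboembolic events without a venous limit. An arterial event would be handled under "Other non-hematologic toxicity assessed as lenalidomide-related" alone only if that sentence were ignored, which is the same conflict again.
- **That everyone dosed on Arm B or after crossover is affected.** They are all subject to the NOTE, but the conflict arises only for those who have a thromboembolic event.

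**Conclusion.** The conflict is real and minor. Read literally, the closing NOTE of 5.5.7 gives the wrong epoetin alfa instruction after a thromboembolic event, and the Table 2 coagulation row omits the resolution condition that 5.5.7 sets. The intended rule, stopping both agents, is stated and is not in dispute. What is missing is the statement that it overrides the NOTE.

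Its reach is limited to patients on combined treatment, by randomization or crossover, who have a thromboembolic event. No count of affected patients or doses is estimated. The clinical data that the protocol cites for this combination come from a pilot in which 18 patients received it and no event was reported (sections 1.2 and 9.2), and how many sites would misread the text is unknown. The endpoint, alpha, power and analysis are not affected.

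The conclusion assumes that the body sentence expresses the sponsor's intent. If the NOTE was meant to prevail after a clot, that would be a different and more serious question, but nothing in the documents suggests it.

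**What to change.** Make two wording changes in one addendum.

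1. Add to the closing NOTE of 5.5.7: *except for thromboembolic events, when epoetin alfa is also stopped (see above)*.
2. Add to the Table 2 coagulation row: *Arm B: also stop epoetin alfa; resume neither agent until resolution with proper prophylaxis, at the investigator's discretion (see 5.5.7)*.

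No separate arterial entry is needed, because the corrected NOTE and the existing body sentence already cover those events. The cost is the addendum text and its notice to sites. There is no statistical cost, and no design decision changes.

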5.5.8 Dose Reduction for Patients with Renal Insufficiency

Defined as creatinine >1.5 mg/dl that does not resolve to grade 1.

Rev. 6/11

[Deleted in Addendum #4]

- Patients with CLcr <60 mL/min and ≥ 30 mL/min should be monitored closely for possibly excess myelosuppression or other toxicity, and dose reduce by 50% upon recovery.

Rev. 6/11

[Deleted in Addendum #4]

Table 2: Dose Modifications for Lenalidomide

System	NCI CTCAE Grade	Action
Coagulation	Venous thrombosis/embolism ≥ Grade 3	
 Hold (interrupt) dose and start anticoagulation; resume lenalidomide at investigator's discretion (maintain dose level).
Skin	Desquamating (blistering) rash	
 Discontinue study treatment.
	Non- desquamating rash Grade 2	
 If Grade 2, interrupt lenalidomide therapy. Resume lenalidomide when the rash resolves to ≤ Grade 1 (decrease one dose level).
	Grade ≥ 3	
 Hold lenalidomide study drug.
Neurology	Neuropathy Grade 3	
 If Grade 3, interrupt lenalidomide 3 therapy. Resume lenalidomide when the neuropathy resolves to ≤ Grade 1 (decrease one dose level).
	Grade 4	
 Hold lenalidomide study drug.
Allergy	Allergic reaction Grade 2	
 If Grade 2, interrupt lenalidomide therapy. Resume lenalidomide when symptoms resolve to ≤ Grade 1 (decrease one dose level).
	≥ Grade 3	
 Hold lenalidomide study drug.
Gastrointestinal	Constipation ≥ Grade 3	
 Hold (interrupt) dose. Initiate bowel regimen, and resume lenalidomide when constipation resolves to ≤ grade 2 (decrease one dose level).
Endocrine	Hyperthyroidism or hypothyroidism	
 Interrupt lenalidomide and initiate appropriate medical therapy. Resume lenalidomide at investigator's discretion (maintain dose level).
Cardiac Arrhythmias	Sinus bradycardia/other cardiac arrhythmia Grade 2	
 Hold (interrupt) dose. Follow at least weekly. If the toxicity resolves to ≤ grade 1 resume at next lower dose level.
	≥ Grade 3	
 Hold lenalidomide study drug.
Other Toxicity	Other non-hematologic toxicity assessed as lenalidomide-related ≥ Grade 3	
 Hold (interrupt) dose. Follow at least weekly. If the toxicity resolves to ≤ grade 2 resume at next lower dose level.

5.6 Supportive Care

- 5.6.1 All supportive measures consistent with optimal patient care will be given throughout the study.
- 5.6.2 Therapies considered necessary for the patient's well being may be administered at the discretion of the Investigator. These therapies include antibiotics, analgesics, antihistamines, or other medications, and transfusions of red blood cells, platelets, or fresh frozen plasma given to assist in the management of complications associated with MDS or study treatment.
- 5.6.3 Packed RBCs: Transfusions of two units of packed RBCs should be considered for decline in hematocrit (HCT) to < 25% or symptoms of cardiovascular compromise. The following **transfusion thresholds and guidelines** are recommended for study participants: HCT < 25%, two units of packed RBCs; HCT < 21%, three units of packed RBCs; HCT < 18%, four units of packed RBCs.
- 5.6.4 Platelets: Eight to ten units of random donor platelets or one cytopheresis unit of single donor platelets should be administered to all subjects with signs of hemostatic failure (i.e., bleeding or petechiae) or life threatening thrombocytopenia (i.e., platelet count < 10,000/mcL).
- 5.6.5 Patients should not receive androgens or steroids for treatment of their anemia or thrombocytopenia as part of supportive therapy.
- 5.6.6 Patients may receive hydrocortisone prophylactically to prevent transfusion reactions. Steroids given for adrenal failure, hormones administered for non-cancer-related conditions (e.g. insulin for diabetes), and intermittent uses of dexamethasone as an antiemetic are permitted concomitantly with study drug. Short courses of steroids to treat study drug-induced skin rashes are also permitted. Use of steroids and reasons should be documented in the E2905 Forms Packet.
- 5.6.7 Each site must have two trained counselors available for counseling all patients receiving lenalidomide supplied by the Division of Cancer Treatment and Diagnosis. Trained counselors must complete training using the online program provided free by the Celgene Pregnancy Prevention Counseling Program (CPPCP). Registration for CPPCP is done by completing the form found in [Appendix XIII](#) and following the directions provided in the email notification. After the training is complete, the counselors must generate a training certificate and provide it to the CTSU for documentation. Sites may not order lenalidomide until documentation for two trained counselors is provided to the appropriate office." The CTSU operations office fax number for CPPCP training certificates: ([name]).

Rev. 7/11
Rev. 4/15

5.7 Duration of Therapy

Patients will receive protocol therapy unless:

- 5.7.1 Extraordinary Medical Circumstances: If at any time the constraints of this protocol are detrimental to the patient's health, protocol treatment should be discontinued. In this event submit forms according to the instructions in the E2905 Forms Packet.
- 5.7.2 Patient withdraws consent.
- 5.7.3 Adverse event(s) (AEs) occur that, in the judgment of the Investigator, may cause severe or permanent harm or which rule out continuation of study drug.
- 5.7.4 Lack of therapeutic effect while on either Arm A (for those patients that are not eligible or do not wish to cross over to Arm B) or Arm B.
- 5.7.5 Patient's disease converts to acute myeloid leukemia or disease progression.
- 5.7.6 Patient is lost to follow-up.

5.8 Duration of Follow-up

For this protocol, all patients, including those who discontinue protocol treatment early, will be followed for response until relapse/progression, and for 6 months from end of protocol treatment. Arm A patients that cross over to Arm B that do not achieve a MER after 16 weeks of combined treatment (i.e. week 32) will discontinue protocol treatment.

Rev. 10/09

6. Measurement of Effect

6.1 **MDS Response Criteria:** Modified International MDS Working Group (IWG) Criteria for Measurement of Response/Treatment Effect in MDS will be used to assess response.

6.1.1 International Prognostic Scoring System (IPSS) for MDS

Prognostic Variable	Survival and AML Evolution Score Value				
	0	0.5	1.0	1.5	2.0
Marrow Blasts (%)	<5	5 to 10	N/a	11 to 20	21 to 30
Karyotype	Good Normal or any 1 of: -Y (del(5q) del(20q)	Intermed. Any other abnormality	Poor chromosome 7 anomalies; Complex: ≥ 3 abnormalities	n/a	n/a
Cytopenias Neutrophil Count < 1800/mcL Platelets < 100,000 mcL Hemoglobin < 10 g/dL	0 or 1	2 or 3	n/a	n/a	n/a

Low: total score = 0

Int-1: total score 0.5-1.0

Int-2: total score 1.5-2.0

High: total score ≥ 2.5

6.1.2 MDS Response Criteria

6.1.2.1 Bone Marrow Response (CR or PR must last ≥ 8 weeks)

1. Complete Remission (CR)

Bone marrow evaluation: Bone marrow showing < 5% myeloblasts with normal maturation of all cell lines, with no evidence for dysplasia (see dysplasia qualifier under peripheral blood evaluation). When erythroid precursors constitute < 50% of bone marrow nucleated cells, the percent of blasts is based on all nucleated cells; when there are ≥ 50% erythroid cells, the percent blasts should be based on the non-erythroid cells.

- Peripheral Blood Counts (Absolute values must last ≥ 8 weeks)
 - Hemoglobin greater than 11 g/dL.
 - Neutrophils 1500/mm³ or more (not on a myeloid growth factor)
 - Platelets 100 000/mm³ or more (not on a thrombopoietic agent)
 - Blasts – ≤ 5%
 - No dysplasia: The presence of mild megaloblastoid changes may be permitted if they are thought to be consistent with treatment effect.

However, persistence of pretreatment abnormalities (e.g., pseudo-Pelger Huet cells, ringed sideroblasts, dysplastic megakaryocytes) is not consistent with CR.

2. Partial Remission (PR)

- All of the CR criteria (if abnormal prior to treatment), except
 - Bone marrow evaluation: Blasts decreased by 50% over pretreatment, or a less advanced MDS WHO classification than pretreatment. Cellularity and morphology are not relevant.

3. Stable Disease

- Failure to achieve at least a PR, but with no evidence of progression for ≥ 2 months.

4. Failure

- Death during treatment or disease progression characterized by worsening of cytopenias, with increase in the percent of bone marrow blasts (as defined in Section [6](#) below), and/or progression to an MDS FAB subtype more advanced than pretreatment.

5. Relapse (following a CR or PR)

- One or more of the following:
 - Return to pretreatment bone marrow blast percentage.
 - Decrement of $> 50\%$ from maximum remission response levels in neutrophils or platelets.
 - RBC transfusion dependence (≥ 2 units RBC transfusions over an 8 week period) or a reduction in hemoglobin concentration by ≥ 2 g/dL in the absence of acute infection, gastrointestinal bleeding, hemolysis, treatment hiatus etc.

6. Disease Progression

- A 50 % increase in blasts, depending on baseline blast percent.
 - For patients with $< 5\%$ blasts: increase to $\geq 10\%$ blasts
 - For patients with 5% to 10% blasts: $\geq 50\%$ increase to $> 10\%$ blasts
 - For patients with 10% to 20% blasts: $\geq 50\%$ increase to $\geq 20\%$ blasts

7. Disease Transformation

- Transformation to AML ($\geq 20\%$ blasts).

